
Sample Size
	
Approximately 60 (i.e., up to 6 cohorts, including expansion cohorts)

Study Centers	Approximately 15 study sites
Statistical Methods Analysis	
The following analysis Populations are defined for the different types of data analysis:
 
• Intent-to-treat (ITT) analysis population, the primary population for the disposition and baseline data summaries.• Pharmacodynamic analysis population, the population for the pharmacodynamic analyses.• Pharmacokinetics analysis population for PK analysis.• Per-protocol analysis population for pharmacodynamics analyses• Safety analysis population for the safety analyses. 
All study-collected data will be summarized by treatment group for the appropriate analysis population, using descriptive statistics. Descriptive statistics for continuous variables will include number of patients (n), mean, standard deviation (SD), median, quartiles (Q1 and Q3), minimum (min) and maximum (max) values. Analysis of categorical variables will include frequency and percentages.
 
Data from COR-001-treated patients from Cohorts not exceeding the MTD will be pooled and data from all placebo patients will be pooled for the pharmacodynamic endpoint analyses.
 
Descriptive analyses by dose in which all placebo patients are pooled will also be conducted.

LIST OF ABBREVIATIONS, DEFINITIONS, AND TERMS

Term	Definition
AE	Adverse event
ALT	Alanine aminotransferase
AST	Aspartate aminotransferase
AUC	Area under the curve
β-hCG	β -Human chorionic gonadotropin hormone
BMP	Bone morphogenic protein
BMPR	Bone morphogenic protein receptor
BP	Blood pressure
BUN	Blood urea nitrogen
CBC	Complete blood count
CHr	Reticulocyte hemoglobin concentration
CFR	Code of Federal Regulations
COR-001	Monoclonal antibody to IL-6
C _{max/min}	Maximum/minimum observed concentration
CRF	Case report forms
CRO	Contract research organization
DLT	Dose-Limiting Toxicity
Dialysis Start Time	The start time of dialysis is defined by the earliest time point recorded on the dialysis flow sheet (or equivalent) with a blood flow rate > 0
Dialysis End Time	Dialysis is considered completed when the dialysis machine shows 0 minutes remaining for the treatment. The end time of dialysis is defined by the latest time point recorded on the dialysis flow sheet (or equivalent) with a blood flow rate = 0 or last recorded blood flow rate, whichever is later.
ECG	Electrocardiogram
ERI	ESA resistance index (ESA weekly dose/targeted dry weight in Kg*hemoglobin in g/dL)
ESA	Erythropoiesis-stimulating agent
FACIT-F [questionnaire]	Functional Assessment of Chronic Illness Therapy – Fatigue
FDA	Food and Drug Administration
FPN	Ferroportin
FSH	Follicle stimulating hormone
GCP	Good Clinical Practice
GLP	Good Laboratory Practices
HAMP	Hepcidin gene
HDL	High density lipoprotein
Hgb	Hemoglobin
HIV	Human Immunodeficiency Virus

Term	Definition
HR	Heart rate
hsCRP	High sensitivity C-Reactive Protein
ICF	Informed Consent Form
ICH	International Conference on Harmonisation
IEC	Independent Ethics Committee
IL-6	Interleukin-6
IL-6R	IL-6 receptor
IND	Investigational new drug
INR	International normalized ratio
iPTH	Intact parathyroid hormone
IRB	Institutional Review Board
IV	Intravenous
IVBP	IV Bag Protectant
IWRS	Interactive Web-Response System
kg	Kilogram
Kt/V	Measure of dialysis clearance and adequacy where K = dialyzer clearance of urea, t = dialysis time, and V – volume of distribution of urea
LDL	Low density Lipoprotein
LHD	Low Hemoglobin density
LLN	Lower Limit of Normal
LVMi	Left Ventricular Mass Index
MCV	Mean corpuscular hemoglobin
mg	Milligram
min	Minute
mL	Milliliter
mITT	Modified Intent-to-Treat
MRI	Myocardial Resonance Imaging
MTD	Maximally Tolerated Dose
NOAEL	No observed adverse effect level
NT-proBNP	N-terminal pro-B-natriuretic peptide
PD	Pharmacodynamic
PK	Pharmacokinetic
PI	Principal Investigator
PPD	Purified Protein Derivative
PT	Prothrombin Time
PTH	Parathyroid Hormone
RBC	Red Blood Cell
RDW	Red cell distribution width
RSf	Red cell size factor

Term	Definition
RR	Respiratory Rate
SAA	Serum amyloid A
SAE	Serious adverse event
SAP	Statistical Analysis Plan
SRC	Safety Review Committee
SOP	Standard Operating Procedure
spKT/V	Single-pool Kt/V
SUSAR	Suspected Unexpected Serious Adverse Reaction
t _{1/2}	Half-life
TB	tuberculosis
TBD	To be determined
TIBC	Total iron binding capacity
TMP	Transmembrane Pressure
TSAT	Transferrin saturation
UFR	Ultrafiltration Rate
ULN	Upper limit of normal
WBC	White blood cells

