Synopsis, Section 4.2	Exclusion Criterion #5	“Inability to undergo a non-contrast magnetic resonance imaging (MRI) scan (e.g., weight over the limits for MRI machine, claustrophobia that cannot be managed, certain metallic indwelling foreign bodies).”	“Inability to undergo a non-contrast magnetic resonance imaging (MRI) scan (e.g., weight over the limits for MRI machine, claustrophobia that cannot be managed, certain metallic indwelling foreign bodies). Requirement for MRI may be exempted by the medical monitor due to practical considerations. In such situations, patients may be enrolled even if they are unable to undergo MRI.”	To allow for practical constraints with obtaining MRIs in all patients

Synopsis, Section 4.2	Exclusion Criterion #12	“Absolute neutrophil count < 2.0 x 10 ⁹ /L at Initial or Full Screening.”	“Absolute neutrophil count < 2.0 x10 ⁹ /L at Initial and Full Screening.”	To allow for enrollment of patients with fluctuations in counts at baseline
Synopsis, Section 4.2	Exclusion Criterion #13	“Platelet count < 100 x 10 ⁹ /L at Initial or Full Screening.”	“Platelet count < 100 x 10 ⁹ /L at Initial and Full Screening.”	To allow for enrollment of patients with fluctuations in counts at baseline
Synopsis, Section 4.2	Exclusion Criterion #25	“iPTH at Screening > 1000 pg/mL”	“iPTH at Screening > 2500 pg/mL”	To increase cut off for patients with otherwise good evidence of marrow function based on other eligibility criteria
Section 5.4.1, Appendix A footnotes	Day -1 randomization	Randomization may be performed on Day -1 (with medical monitor approval)	Randomization may be performed on Day -1 (no medical monitor approval needed)	To facilitate site logistics
Synopsis, Section 11.4.4	Free IL-6	Primary PD endpoint	Exploratory PD endpoint	Technical limitations of assay
Appendix A and Appendix D	Additional time points for serum albumin added (pre-albumin removed from these same time points)	Week -2, Days 1, 36, 78, 162	Week -2, Days 1, 36, 64, 78, 92, 120, 162	To better define the time course of changes in albumin without increasing blood volume taken from patients
Appendix A	Screening Period window	-	Allowance of the Medical Monitor to approve an increase in the Screening Period window by up to 12 days	To facilitate site logistics and central MRI readings

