--	---

Exclusion Criteria:	
To be eligible for study enrollment, potential study patients must not meet any of the following exclusion criteria:
 
1. Any indwelling vascular catheter (including that used for dialysis) or anticipated use of an indwelling catheter anytime during the study (including the Initial Screening and Full Screening Periods).2. Patients for whom a central venous catheter is used within 2 weeks prior to Step 2 of the Initial Screening Period (blood draw for IL-6, see Section 5.2) will be also be considered screening failures. Use of systemic immunosuppressive drugs during the Full Screening Period or anticipated use of such drugs any time during the study. Note: Use of otic, ophthalmic, inhaled, and topical corticosteroids or local corticosteroid injections are not exclusionary. Oral prednisone up to 5 mg per day is (or equivalent) is permitted.3. Clinical evidence or suspicion of active or smoldering infection (e.g., diabetic foot ulcer) or use of systemic antibiotics, systemic antivirals, or systemic antifungals within 2 weeks prior to Step 2 of the Initial Screening Period (blood draw for IL-6, see Section 5.2), during the Initial Screening Period, or the Full Screening Period. ("Systemic" is defined as oral or intravenous drugs that are absorbed into the circulation.)4. Hospitalization or outpatient procedures within 2 weeks prior to Step 2 of the Initial Screening Period (blood draw for IL-6, see Section 5.2), during the Initial Screening Period, or the Full Screening Period unless approved by the Medical Monitor. Note: Please contact the Medical Monitor for approval and determination of timing of IL-6 measurements if considering enrolling patients with hospitalizations or outpatient procedures during this time frame.5. Inability to undergo a non-contrast magnetic resonance imaging (MRI) scan (e.g., weight over the limits for MRI machine, claustrophobia that cannot be managed, certain metallic indwelling foreign bodies). Requirement for MRI may be exempted by the medical monitor due to practical considerations. In such situations, patients may be enrolled even if they are unable to undergo MRI.6. Positive tuberculosis blood test at Screening7. Evidence of HIV-1 or HIV-2 infection by serology at Screening.8. Hepatitis B or C by serology (i.e. Hepatitis B Surface Antigen or Hepatitis C antibody positive) at Screening.9. AST or ALT > 2.5x ULN at Screening.10. History of liver cirrhosis or home oxygen use (other than nocturnal-only oxygen for those with sleep apnea).11. History of gastrointestinal ulceration or active diverticulitis in the 1 year prior to Initial Screening.12. Absolute neutrophil count < 2.0 x 10⁹/L at Initial and Full Screening.13. Platelet count < 100 x 10⁹/L and Initial or Full Screening.

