3.6 Safety Plan and Monitoring

The study design, including entry criteria, planned interim safety data reviews, and planned conduct includes a number of elements intended to minimize risk, intended to better monitor for or to mitigate risk to study patients:

- All Study Drug doses will be administered in either a hemodialysis unit or Phase 1 research unit with hemodialysis capabilities in the presence of trained healthcare professionals and resuscitative equipment.
- Patients will be in contact with healthcare professionals three (3) times per week during their hemodialysis treatments, actively observed by study staff for adverse events such as infections, and undergo regular safety monitoring (i.e., vital signs, ECG, physical examination, laboratory evaluations).

- All principal investigators will be nephrologists and therefore skilled in the management of dialysis patients.
- Dose escalation will occur by cohort upon formal safety review as described above. An every-other week dose administration paradigm was chosen based on formal PK/PD modeling to allow for timely withdrawal of investigative therapy if required. The dose escalation decision will also take into account accrued PK/PD data from the study, so that the planned doses can be adjusted, if necessary.
- Dose-Limiting Toxicity criteria and rules for MTD will be pre-defined. Because of the high background frequency of Grade 2 and 3 adverse events in hemodialysis patients (not dissimilar from cancer populations), the DLT threshold will be defined using a threshold of \geq Grade 3 events.
- Initial dosing in each cohort examining a higher dose than studied in a prior cohort will be in two sentinel patients who will be observed for at least 48 hours for early adverse effects before additional patients are dosed.
- Patients will be required to have an absolute neutrophil count of $> 2 \times 10^9/L$ during screening, and decrease in neutrophil count will be treated as a safety event of interest.
- Patients at high risk for infection such as those with temporary hemodialysis catheters, recent or current active infections, smoldering infections, serologic evidence of Hepatitis B or C or HIV, history of tuberculosis (or positive interferon gamma release testing), and baseline neutropenia will be excluded.

Please see the [Guidance to Investigators section](#) of the Investigator's Brochure for a description of safety findings from other IL-6 monoclonal antibodies and guidance for clinical monitoring.

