10. History of liver cirrhosis or home oxygen use (other than nocturnal-only oxygen for those with sleep apnea).
11. History of gastrointestinal ulceration or active diverticulitis in the 1 year prior to Initial Screening.

12. Absolute neutrophil count $< 2.0 \times 10^9/L$ at Initial and Full Screening.
13. Platelet count $< 100 \times 10^9/L$ at Initial and Full Screening.
14. Expected to receive any investigational drug or any of the exclusionary drugs listed in [Appendix B](#) during the Treatment Period or Safety Follow-Up Period.
15. Received an investigational drug within 30 days prior to the start of the Full Screening Period.
16. Known allergy to the Study Drug or any of its ingredients.
17. Currently breastfeeding
18. Any condition that could interfere with, or for which the treatment might interfere with, the conduct of the study or interpretation of the study results, or that would in the opinion of the Investigator increase the risk of the patient's participation in the study. This would include but is not limited to alcoholism, drug dependency or abuse, psychiatric disease, epilepsy, anemia attributable to a primary hematologic disease (e.g., sickle cell anemia), or any unexplained blackouts.
19. Actively treated or active malignancy (other than non-melanoma skin cancers or cervical carcinoma in situ considered cured at the time of Full Screening) during the 1 year prior to Full Screening.
20. Myocardial infarction during the 2 months prior to Full Screening or during Screening.
21. Known or suspected occult or active bleeding other than that related to the hemodialysis procedure.
22. Received a red blood cell or whole blood transfusion within 2 months prior to Full Screening or anticipated to receive a blood transfusion at any time during the study.
23. Have inflammatory bowel disease that has been clinically active during the 3 months prior to Full Screening or bone marrow or organ transplant.

Note: Patients with a previously explanted kidney transplant are eligible as are those who have an implanted kidney transplant, but have not received immunosuppression for at least 6 months prior to Full Screening.
24. Anticipated to receive an organ transplant during the time frame of the study.
25. iPTH at Screening > 2500 pg/mL.

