4.4 Dose-Limiting Toxicities, Maximum Tolerated Dose, and Stopping Rules

Prior to dose escalation (i.e., higher total dose than studied in the preceding cohorts), there will be a formal safety review by the Safety Review Committee. The safety review required for dose escalation will include 21 days of treatment data from the preceding cohort(s).

Dose-Limiting Toxicities are defined as follows:

1. Confirmed Grade 3 neutropenia and representing a decline of > 25% from baseline
2. Serious adverse events of infection in the presence of confirmed Grade 2 or higher new onset lymphopenia or new onset neutropenia.
3. \geq Grade 3 ALT or AST
4. \geq Grade 4 hematologic toxicity
5. \geq Grade 3 non-hematologic toxicity

DLT will be defined as any toxicity the relationship of which to the investigational agent cannot be ruled out as follows:

- With the exception of Grade 3 non-hematologic events, Grade 3 (or higher) CTCAE toxicity of above events having an assessed relationship to the Study Drug of “definitely”, “probably”, “possibly”, or “unlikely” will be considered DLTs.

Note: “non-hematologic events” refer to DLT criteria 1, 2, 3, and 5 above.

- Grade 3 non-hematologic toxicities having an assessed relationship to the Study Drug of “definitely”, “probably” or “possibly” will be considered DLTs.

In addition, dose-escalation may be halted for any safety trend believed to be dose-related that would pose an unacceptable risk if dose were escalated.

If more than 2 of 8 COR-001-treated patients in a cohort experience a DLT, the MTD will be exceeded and stopping criteria for that dose will have been met.

In addition, if 1 of 8 COR-001-treated patients in a cohort experiences a Grade 4 or 5 DLT, the dose will not be escalated.

Stopping Rules for Individual Patients

Severe (i.e., \geq Grade 3): infusion-related reactions, cardiopulmonary infusion reactions, anaphylaxis, or hypersensitivity (see [Section 8.2](#))

Stopping Rules for the Entire Study

If ≥ 5 COR-001-treated patients develop anaphylaxis at any point during the entire study, enrollment and further dosing will be stopped.

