9.3 Adverse Events of Special Interest

The following adverse events of special interest must be reported to the Sponsor within 24 hours of the Investigator's awareness, even if not meeting the definition of a serious adverse event:

- Severe infusion-related reactions (see [Section 8.2](#)).
- Hypersensitivity reaction during the Study Drug infusion (see [Section 8.2](#)).
- Anaphylaxis (see [Section 8.2](#)) occurring at any time, even if considered unrelated to the Study Drug

A CRF for the collection of the details of such reactions will be available in the EDC.

Neutropenia, Grade 2 or higher [i.e., absolute neutrophil count < 1500/mm³ and decline by at least 25% from Baseline] are also events of interest and these will be separately summarized by treatment group and dose.

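### The neutrophil, platelet and tuberculosis exclusions conflict within the protocol, and low neutrophil baselines let the 25% decline clause leave some neutropenia out of the safety counts

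*Protocol*

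**What the plan says.** **Eligibility**

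- Exclusion 12 (neutrophils) has the same joint condition in the Synopsis, "Absolute neutrophil count < 2.0 x 10⁹/L at Initial and Full Screening", and in Section 4.2. The Amendment 3 summary gives the reason for that wording: "To allow for enrollment of patients with fluctuations in counts at baseline".
- Exclusion 13 (platelets) reads "Platelet count < 100 x 10⁹/L and Initial or Full Screening" in the Synopsis. In Section 4.2 the same criterion applies "at Initial and Full Screening".
- Section 3.6 requires a neutrophil count above 2 × 10⁹/L during screening. Its list of patients at high infection risk ends "history of tuberculosis (or positive interferon gamma release testing), and baseline neutropenia will be excluded".
- Exclusion 6 rests only on a positive tuberculosis blood test at Screening, in both the Synopsis and Section 4.2.

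**Neutropenia counts**

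- DLT criterion 1 (Section 4.4) is "Confirmed Grade 3 neutropenia and representing a decline of > 25% from baseline".
- The event of interest in Section 9.3 needs a count below 1500/mm³ together with a "decline by at least 25% from Baseline". Section 9.3 promises a separate summary by treatment group and dose.
- SAP 1.2.2 and 8.2 list only infusion-related reactions, hypersensitivity and anaphylaxis as events of interest. Neutropenia is not among them.
- Baseline is the latest pre-dose evaluation in protocol Section 11.3.3, and the mean of Week -1 and Day 1 for laboratory parameters in SAP 8.4. Neither definition has a neutrophil floor.

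**The concern.** Section 3.6 is where the protocol explains how risk is contained, and two of its neutrophil statements do not describe the patients whom exclusion 12 admits. Someone relying on Section 3.6 would believe that a patient with a low count at Full Screening cannot be dosed, and the criteria say otherwise. For platelets, the decision on a patient with one low count depends on whether the Synopsis or Section 4.2 is open. For tuberculosis, a patient with a past history and a negative blood test is excluded by Section 3.6 and eligible under exclusion 6.

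The statistical consequence comes through baseline. Both neutropenia definitions add a relative decline to an absolute limit. A patient who starts low can cross the absolute limit without a 25% fall and is then not counted. Section 4.4 treats the maximum tolerated dose as exceeded at more than 2 of 8 treated patients, so one event left out can turn 3 of 8 into 2 of 8. Section 3.7 says that anti-IL-6 therapies lower neutrophil counts.

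**Working it through.** The plan states no figure on this point, so there is nothing to reproduce. Counts are in 10⁹/L.

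**Step 1: exclusion 12 against Section 3.6.** Section 3.6 can be read as above 2 throughout screening, or as above 2 at least once.

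| Initial | Full | Exclusion 12 as written | 3.6, throughout | 3.6, at least once |
|---|---|---|---|---|
| 2.4 | 2.4 | admitted | met | met |
| 2.4 | 1.4 | admitted | not met | met |
| 2.0 | 1.4 | admitted | not met | not met |
| 1.4 | 1.4 | excluded | not met | not met |

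The lenient reading rescues the second row only for the numeric requirement. It does not satisfy the separate statement that baseline neutropenia is excluded. The third row fails on either reading, because one text uses below 2.0 and the other above 2.

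**Step 2: which count becomes baseline.** Appendix A draws hematology at Initial Screening, Week -2, Week -1 and Day 1. The Initial Screening count, which can be the one that qualifies the patient, does not enter the SAP 8.4 baseline and is not the latest pre-dose value when later samples exist.

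- Under *and*: Initial 2.1, Week -1 1.2, Day 1 2.0. The patient is admitted, with SAP 8.4 baseline (1.2 + 2.0)/2 = 1.6.
- Under *or*: every screening count at least 2.0, Week -1 2.0, Day 1 1.4. The patient would also be admitted, with SAP 8.4 baseline (2.0 + 1.4)/2 = 1.7, and 1.4 under protocol 11.3.3.

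The *and* wording therefore makes low baselines more likely but is not their only source.

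**Step 3: event of interest (Section 9.3).** With baseline B, an event needs a count below 1.5 and at or below 0.75 × B. The clause starts to bind when 0.75 × B = 1.5, that is at B = 1.5/0.75 = 2.0.

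| B | 0.75 × B | Counts below 1.5 that are left out |
|---|---|---|
| 2.5 | 1.875 | none |
| 2.0 | 1.5 | none |
| 1.9 | 1.425 | above 1.425 |
| 1.8 | 1.35 | above 1.35 |
| 1.6 | 1.20 | above 1.20 |

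For example, 1.9 to 1.45 is a fall of 0.45/1.9 = 23.7%, and 1.6 to 1.25 is 0.35/1.6 = 21.9%. Neither is counted.

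**Step 4: DLT criterion 1 (Section 4.4).** Section 9.5 names CTCAE 4.03, but the documents do not print the Grade 3 neutrophil limit, so it is taken as an assumption G. Break-even is B = G/0.75.

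- G = 1.0: B = 1.33. A fall from 1.2 to 0.95 is 0.25/1.2 = 20.8%, so criterion 1 is not met. A fall from 1.8 to 0.99 is 0.81/1.8 = 45%, so it is.
- G = 0.5: B = 0.67.

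The DLT count is thus affected only at much lower baselines than the event of interest.

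**The case against.** Four counter-arguments carry weight.

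1. **The loosening was deliberate, and Section 3.6 is narrative.** Exclusion 12 is identical in the two criteria lists, so sites are not told different things there. This stands as far as it goes. It does not remove the conflict with the current text of Section 3.6. The platelet mismatch lies between the two criteria lists themselves, although the Synopsis sentence is visibly garbled.
2. **The clause may be working as intended.** A patient who starts low and stays low has arguably shown no drug effect. If every baseline were at least 2.0, the clause in Section 9.3 would do nothing, so it can be read as written for low baselines. This is a good reason not to delete the clause, and to show the counts both ways.
3. **The neutropenia is not hidden.** SAP 8.4 presents shifts to the worst CTC grade with no decline clause, and the hematology panel includes the white-cell differential. DLT criterion 4 covers Grade 4. Criterion 2, serious infection with new-onset neutropenia or lymphopenia, carries no decline clause either. Section 4.4 also allows escalation to be halted for a safety trend. All of this stands. None of it changes the event-of-interest or criterion 1 counts.
4. **Reach may be small.** Amendment 3 records actual doses for Cohorts 1 to 5 as completed or ongoing, and the Synopsis plans up to 6 cohorts. The *and* rule would then bear mainly on the last cohort and any unenrolled part of the fifth. That is a fair inference, though the documents do not give enrolment by date.

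**Conclusion.** The protocol contradicts itself on three eligibility points: neutrophils (exclusion 12 against Section 3.6), platelets (Synopsis against Section 4.2) and tuberculosis history (exclusion 6 against Section 3.6). The 25% clause leaves out some absolute neutropenia when baseline is below 2.0 for the Section 9.3 event. For DLT criterion 1 the corresponding baseline is about 1.33 (Grade 3 assumed below 1.0) or 0.67 (below 0.5). How many patients fall in these ranges cannot be derived from the documents. The SAP also plans no event-of-interest summary of neutropenia, although Section 9.3 promises one.

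A reader might infer more, and the documents do not support it:

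- *That the 25% clauses assume a baseline of at least 2.0.* No section says so. The match with 2.0 is arithmetic, holds only for the Section 9.3 event, and does not extend to the DLT clause.
- *That the change to exclusion 12 created the gap.* Day 1 values enter baseline and are not screening values, so baselines below 2.0 were possible under *or*.
- *That toxicity is concealed or understated where risk is highest.* The events are left out of two counts but should be visible in the grade-shift table, and nothing in the documents shows that these patients carry the highest risk.

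The point should be corrected because it touches the primary safety count, but it does not undermine the design.

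**What to change.** 1. Reconcile exclusion 12 (Synopsis and Section 4.2) with Section 3.6, exclusion 13 between the Synopsis and Section 4.2, and exclusion 6 with Section 3.6, so that each criterion has one rule throughout. Which rule is for the sponsor to decide.
2. Add to SAP 1.2.2 and 8.2 the summary of Grade 2 or higher neutropenia, by treatment group and dose, that protocol Section 9.3 promises. This is a new summary, since SAP 8.2 has no neutropenia row to split.
3. Tabulate that summary, and confirmed Grade 3 neutropenia under SAP 8.1, both with and without the 25% clause, by baseline count below versus at or above 2.0 × 10⁹/L. State in the table which baseline definition is used.
4. Give the Safety Review Committee both counts.

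The cost is a wording correction in the protocol and one added safety table from data already collected. No extra visits or samples are needed.
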